8.1.1. DEFINITION OF ADVERSE EVENTS (AE) AND SERIOUS ADVERSE EVENTS (SAE)

An adverse event (AE) or effect is defined as any untoward and unintended medical occurrence experienced by a clinical study subject. An AE can therefore be any unfavorable and unintended sign, symptom, or disease temporally associated with the use of the investigational product, whether or not related to the product.

The following events will be considered to be serious adverse events (SAE) and must immediately and without delay (within 24 hours) be reported to the study Sponsor by fax and/or email. These events must be reported whether or not the Investigator believes they are related to study procedures, activities or device:

- Death (the investigator will provide a copy of any post-mortem findings, including histopathology reports if available).
- Life-threatening event or injury
- Disability significant, persistent, or permanent change, impairment, or damage or disruption in the subject's body function/structure, physical activities or quality of life

Version 2.0 tember 7, 2017

- Necessitate immediate medical or surgical intervention to:
 - Preclude permanent impairment of a body function or permanent damage to a body structure; or
 - Relieve unanticipated temporary impairment or damage.
- Prolongation of a hospitalization
- New hospitalization

8.1.2. DEFINITION OF ADVERSE DEVICE EFFECT (ADE) AND SERIOUS ADVERSE DEVICE EFFECT (SADE)

An Adverse Device Effect (ADE) is defined as any untoward or unintended response to a medical device. This definition includes any event resulting from insufficiencies or inadequacies in the instructions for use or the deployment of the device. This definition also includes any event that is a result of user error. A Serious Adverse Device Effect (SADE) is an adverse device effect that has resulted in any of the consequences characteristic of a serious adverse event or that might have led to any of these consequences if suitable action had not been taken or intervention had not been made or if circumstances had been less opportune. All SADEs must immediately and without delay (within 24 hours) be reported to the study Sponsor by fax and/or email.

8.1.3. DEFINITION OF UNANTICIPATED ADVERSE DEVICE EFFECT (UADE)

An unanticipated adverse device effect (UADE) is defined as any serious adverse effect on health or safety or any life-threatening problem or death caused by, or associated with, a device, if that effect, problem, or death was not previously identified in nature, severity, or degree of incidence in the investigational plan or application (including a supplementary plan or application), or any other unanticipated serious problem associated with a device that relates to the rights, safety, or welfare of subjects (21 CFR 812.3(s)).

8.2. CLASSIFICATION OF AN ADVERSE EVENT

8.2.1. SEVERITY OF EVENT

The following guidelines will be used to describe the severity of an event:

- Mild Awareness of the event, may cause no or minimal interference with the subject's daily life.
- **Moderate** Discomfort enough to cause a noticeable impact on the subject's daily life.
- Severe Incapacitation or significant impact on the subject's daily life.

8.2.2. RELATIONSHIP TO STUDY DEVICE/PROCEDURES

Two types of relationships will be assessed:

- 1. Related to the Latera device or Latera device-specific procedure, including Implant delivery
- 2. Related to concomitant procedures, such as septoplasty and turbinate reduction

The clinician's assessment of an AE's relationship to the study device, implant procedure and/or the concomitant procedure(s) is part of the documentation process, but it is not a factor in determining what is or is not reported in the study. If there is any doubt as to whether a clinical observation is an AE, the event should be reported. All AEs must have their relationship to the Latera study device or Latera device procedure assessed.

Spirox Latera™ implant support of lateral wall cartilage (LATERAL-OR) study	Version 2.0
SPI-CP-301	September 7, 2017

For all collected AEs, the clinician who examines and evaluates the subject will determine the AE's causality based on temporal relationship and his/her clinical judgment. The degree of certainty about causality will be graded using the categories below.

- **Definitely Related** The event is definitely related to the study device/procedure or concomitant procedure
- **Probably Related** The event is probably related to the study device/procedure or concomitant procedure; or the event cannot be explained by other condition or illness.
- **Possibly Related** The event is possibly related to the study device/procedure or concomitant procedure, but not likely.
- **Unlikely Related** The event is unlikely related to the study device/procedure or concomitant procedure.
- Not Related The event is definitely not related to the study device/procedure or concomitant procedure.

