4.2. STUDY ENDPOINTS

4.2.1. PRIMARY ENDPOINTS

Primary Efficacy Endpoint: Proportion of treatment responders at 6 months post procedure.

• Responder is defined as subject that has at least 1 NOSE class improvement or at least 20% NOSE score reduction

Primary Safety Endpoint: Nasal procedure and Latera device-related adverse events through 6 months.

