10.2. STATISTICAL HYPOTHESES

Primary Efficacy Endpoint:

• The primary efficacy endpoint is the proportion of treatment responders at 6 months post procedure. Since there is no direct comparison group in this study, the primary efficacy hypothesis is a superiority comparison to a target proportion:

Null Hypothesis H₀: the proportion of responders at 6 months is = 0.50, versus Alternative Hypothesis H_A: the proportion of responders at 6 months is \neq 0.50

• There are no other formal statistical hypotheses.

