10.4.4. SAFETY ANALYSES

Two analysis sets will be used to *summarize* adverse events. The ITT analysis set will be used to summarize acute adverse events (through 1 month post procedure), and the mITT analysis set will be used to summarize adverse events over the entire duration of follow-up. The primary safety reporting time-point is 6 months post-implant.

The overall incidence (i.e., number and percent of subjects with 1 or more adverse event in each class) of adverse events, serious adverse device events, serious adverse events, fatal adverse events, and device related events (e.g., possibly, probably or definitely related) will be calculated for the acute phase, through 6 months post-procedure and for the entire duration of follow-up. The overall incidence of mild, moderate and severe events will be calculated by considering the most severe event for each subject.

In addition, the overall incidence for each adverse event type will be calculated. The adverse event types will be classified according to the following categories:

- Excessive Inflammation
- Significant Foreign body sensation
- Excessive Pain or discomfort
- Infection
- Implant Extrusion, defined as body rejection of implants
- Implant Retrievals, defined as surgeon or subject initiated removal of implants not associated with body rejection of implant
- Implant bent or fractured
- Implant loose
- Implant migration
- Skin irritation
- Hematoma
- Unintended perforation of the skin
- Other

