#### 5.1. ADVERSE EVENTS

Adverse events (AEs) will be coded. Adverse events through 7 days post procedure will be summarized for the ITT analysis set, and cumulative summaries will be produced for the mITT analysis set.

Categories of adverse events include:

- Device-related AEs
- Implant procedure-related AEs
- Serious AEs
- Adverse Device Effect (ADE)
- Device retrievals
- Moderate or Severe AEs

Summaries may also be produced by follow-up interval.

For each AE category, the percentage of subjects who experienced at least one occurrence of the given event will be calculated. Overall frequency by coded type will also be summarized. In addition, each AE will be listed for each subject. These listings will include onset interval, relationship to procedure and implant, severity, whether the event is an ADE, SADE or SAE, onset and resolution dates, action taken and outcome.

If the timing of events such as implant retrieval is of interest, this will be analyzed using Kaplan-Meier techniques.

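### The causality scale gives no criterion to separate possibly from unlikely related, and the plan's only stated cut for device-related events falls between those two grades

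*Protocol*

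**What the plan says.** Protocol 4.2.1 sets the primary safety endpoint as "Nasal procedure and Latera device-related adverse events through 6 months". Relatedness is therefore part of what defines the endpoint.

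Protocol 8.2.2 grades certainty about causality in five ordered steps: definitely, probably, possibly, unlikely and not related. *Possibly Related* reads "The event is possibly related to the study device/procedure or concomitant procedure, but not likely". *Unlikely Related* reads "The event is unlikely related to the study device/procedure or concomitant procedure". The clinician who examines the subject "will determine the AE's causality based on temporal relationship and his/her clinical judgment"; no other criterion is given.

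Protocol 10.4.4 summarises, among other things, "device related events (e.g., possibly, probably or definitely related"). It gives no corresponding list of grades for events related to the procedure.

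SAP 5.1 names "Device-related AEs" as a category, and implant procedure-related events as another, without saying which causality grades put an event in either. It also plans a listing of every event that shows "relationship to procedure and implant, severity, whether the event is an ADE, SADE or SAE".

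**The concern.** A causality scale matters most where the analysis cuts it. Here the grade just inside the cut and the grade just outside it are both described as a link that is not likely. An examining clinician who thinks an event is probably not due to the implant, but cannot exclude it, can defend either grade from the definitions. One choice puts the subject in the related-event count and the other leaves the subject out.

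Such events are unlikely to be rare. Implants may be placed together with septoplasty or turbinate reduction, and Appendix II of the protocol reports that 89% of commercial cases were combined with these procedures. Protocol 2.3.2 lists infection and pain among the risks of both septoplasty and the implant, and hematoma as a reported complication of the former and a risk of the latter.

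The study is open label at approximately 25 sites. The Medical Monitor reviews events and decides expectedness, but the documents do not say that causality is re-graded centrally. At stake is how well the reported related-event rate can be interpreted. Appendix II says the data may be used for regulatory applications and publications.

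**Working it through.** The plan states no figure on this point, so there is none to reproduce. The check is a comparison of text, followed by one line of arithmetic for scale.

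**Step 1: the two definitions.** Reduced to content, *Possibly Related* (Protocol 8.2.2) says that a link is possible and not likely. *Unlikely Related* says that a link is unlikely. An unlikely link is also still possible, because *Not Related* is a separate, lower grade. The same event can satisfy both. Neither definition mentions an alternative cause, timing or plausibility, which could have divided them. What remains is the order of the labels.

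**Step 2: the gap above.** The grade above *Possibly Related* is *Probably Related*. An event for which the implant and another cause seem about equally plausible is neither probable nor unlikely, and no definition fits it well. This comes from the same qualifier in the *Possibly Related* definition.

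**Step 3: where the cut falls.** Protocol 10.4.4 puts the upper three grades in the device-related group. By implication the lower two are outside. The boundary lies exactly between the two overlapping grades.

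**Step 4: how firm the cut is.** It is given as an example, for device-related events only. The endpoint in 4.2.1 also includes nasal procedure-related events, for which no cut appears. SAP 5.1 supplies neither.

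**Step 5: scale.** Inputs:
- Safety denominator: SAP 2.2.1 bases cumulative events at 6 months on the mITT set.
- Size of that set: the SAP sample size section plans at least 150 and up to 170 enrolled. I assume the mITT set lies in that range.

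If *k* subjects have no other related event and their one event moves across the cut, the rate changes by *k*/N.
- For *k* = 1 and N = 170: 1/170 = 0.59 percentage points.
- For *k* = 1 and N = 150: 1/150 = 0.67 percentage points.

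The documents give no expected number of events by grade, so *k* cannot be estimated. A subject who also has an event graded *Probably* or *Definitely Related* is counted either way and does not contribute to *k*.

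**The case against.** The best case for leaving the text alone has four parts.

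- **The grades are ordered.** The label affirms a possibility, and the qualifier can be read as separating *Possibly* from *Probably* above it rather than from *Unlikely* below it. This stands in part: many clinicians will treat *Possibly* as the stronger grade, so it would be too much to call the two grades identical. But definitions exist so that clinicians need not rely on the label alone, and these do not help at this boundary.
- **Nothing inferential depends on it.** Protocol 10.2 says of the efficacy test that "There are no other formal statistical hypotheses", and no safety performance goal is set. This stands. Type I error, power and any pass or fail decision are untouched.
- **Other outputs do not use the grade.** Protocol 10.4.4 reports overall, serious and fatal events, severity, and incidence by type, including extrusion, retrieval, migration and hematoma. Protocol 8.1 collects non-serious head and neck or respiratory events whatever their relation, and the SAP listings let a reader recount. This stands as mitigation. It does not correct the summary rate. After 12 months it helps less, because Protocol 7.1.4 then limits collection to adverse device effects.
- **Including *Possibly* is already the inclusive choice.** True, but the SAP does not confirm it.

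A reader might go further and put a relative size on the effect, for instance by starting from the German study in Protocol 2.2 (4 of 30 subjects with a device-related event, 13.3%) and adding a number of borderline subjects. The documents do not support that. No count of borderline events is given, the causality scale of that study is not shown, and its subjects had no septal or turbinate treatment, whereas the present endpoint includes nasal procedure-related events. Nor do the documents show that grading will in fact differ between sites or lean in the device's favour; they only leave room for it.

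**Conclusion.** The point holds as a defect in the definition of a descriptive primary endpoint. Two adjacent causality grades have no criterion between them other than label order, the only stated cut falls there, and the SAP fixes no mapping for device or procedure events. The related-event rate therefore depends partly on a choice the plan does not define.

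The total size is unknown. The effect per subject is about 0.6 to 0.7 percentage points, on the assumptions that the mITT set is between 150 and 170 and that the subject has no other related event. The efficacy conclusion and all formal tests are unaffected. The change is worth making because it is cheap and concerns the headline safety result, not because a wrong safety conclusion has been shown to be likely.

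**What to change.** 1. **Protocol 8.2.2 and the matching eCRF help text.** Remove the qualifier at the end of the *Possibly Related* definition and give the two grades distinct content. For example, *Possibly*: a causal link is a reasonable possibility, although another cause is also plausible. *Unlikely*: another cause is more probable.
2. **SAP 5.1.** State as a rule, not as an example, that definitely, probably and possibly count as related, for both the device and the procedure categories.
3. **SAP 5.1, 6-month safety table.** Add one sensitivity row that also counts *Unlikely Related* events as related. It uses grades already collected and shows how far the rate could rise if events just below the cut belonged above it, including events graded under the existing wording.

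The cost is a small rewording, one table row, and a reported related-event rate that may be slightly higher. Some clinical judgment will remain at the boundary under any wording; the sensitivity row makes its effect visible.

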8.2.3. EXPECTEDNESS

The Medical Monitor will be responsible for determining whether an AE is expected or unexpected. An AE will be considered unexpected if the nature, severity, or frequency of the event is not consistent with the risk information previously described for the device as well as concomitant procedures (septoplasty and/or turbinate reduction).

Refer to section 2.3.2 for list of expected risks.

8.3. TIME PERIOD AND FREQUENCY FOR EVENT ASSESSMENT AND FOLLOW-UP

The occurrence of an AE or SAE may come to the attention of study personnel during study visits and interviews of a subject presenting for medical care, or upon review by a study monitor.

All device or procedure-related AEs, including local and systemic reactions not meeting the criteria for SAEs, will be captured on the appropriate CRF. Information to be collected includes event description, time of onset, clinician's assessment of severity, relationship to study product (assessed only by those with the training and authority to make a diagnosis) or concomitant procedures, and time of resolution/stabilization of the event. All AEs occurring while on study must be documented appropriately regardless of relationship. All AEs will be followed to adequate resolution.

Any medical condition that is present at the time of the participant's procedure will be considered as a baseline condition or comorbidity, and will not reported as an AE. However, if the subject's condition deteriorates at any time during the study, and the condition is procedure/device related, it will be recorded as an AE. AEs will be recorded in the data collection system throughout the study.

Changes in the severity of an AE will be documented. AEs characterized as intermittent require documentation of onset and duration of each episode.

At each study visit, the investigator will inquire about the occurrence of AE/SAEs since the last visit. Events will be followed for outcome information until resolution or stabilization.

8.4. **REPORTING PROCEDURES**

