8.6. SAFETY OVERSIGHT

Adverse events will be reviewed periodically by the Medical Monitor. For any reported SAE, the Medical Monitor and Scientific Advisory Board members will review the relevant materials and may issue a recommendation to terminate the study as described above.

If this recommendation is reached, then the PI, study sites and IRBs will be notified. In addition, Spirox will follow the MDR reporting requirements pursuant to (21 CFR 803.19(a)(2)).

Spirox Latera™ implant support of lateral wall cartilage (LATERAL-OR) study SPI-CP-301

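### Protocol 8.3 records worsening of a baseline condition as an adverse event only if it is procedure- or device-related, which contradicts 8.1, 8.1.1, 8.2.2 and another sentence of 8.3

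*Protocol*

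**What the plan says.** Protocol 8.3 sets a rule for conditions already present when the procedure takes place. Such a condition "will be considered as a baseline condition or comorbidity, and will not reported as an AE". One exception follows: if the subject's "condition deteriorates at any time during the study, and the condition is procedure/device related, it will be recorded as an AE". The exception therefore has two joint requirements, deterioration and relatedness.

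Other parts of the protocol take a different line:

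- **8.3, preceding paragraph:** "All AEs occurring while on study must be documented appropriately regardless of relationship".
- **8.2.2, on the causality assessment:** "it is not a factor in determining what is or is not reported in the study". It adds: "If there is any doubt as to whether a clinical observation is an AE, the event should be reported".
- **8.1.1:** an AE is defined without reference to relationship, and serious events "must be reported whether or not the Investigator believes they are related" to the study.
- **8.1:** the collection scope is all SAEs, adverse device effects (ADEs) and serious adverse device effects (SADEs), all non-serious device- and procedure-related AEs, and all non-serious head-and-neck and/or respiratory AEs. The last group has no relatedness filter.
- **8.4.2:** all SAEs and SADEs go to the sponsor within 24 hours, with an AE form.

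On who decides, 8.2.2 states that "the clinician who examines and evaluates the subject will determine the AE's causality based on temporal relationship and his/her clinical judgment". On oversight, 8.6 states: "For any reported SAE, the Medical Monitor and Scientific Advisory Board members will review the relevant materials". The SAP (5.1) lists AE categories and summaries but says nothing about worsening of baseline conditions.

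**The concern.** The deterioration sentence is the only text that deals directly with worsening of a pre-existing condition. A coordinator asking whether worsened obstruction is an AE would naturally go to it. Applied as written, it asks for a causality judgement first and a record second, the reverse of the order in 8.2.2.

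This population makes the order matter. Inclusion criterion 1 requires a NOSE score of at least 55, so every one of up to 170 subjects has nasal obstruction at baseline. Septal deviation, turbinate hypertrophy and nasal allergy are permitted at entry, and the plan collects data on each. Section 2.3.2 lists continued obstruction among the septoplasty risks and edema with subsequent obstruction among the turbinate risks. A harm of that kind can look like the underlying disease.

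The study is open label (10.6), and AE source documents are signed off by the procedure-trained investigator (8.4.1). At stake are the completeness of the AE counts in 10.4.4 and the possibility of anyone later checking a judgement that an event was unrelated.

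**Working it through.** The plan gives no figure on this point and no arithmetic applies. The check is to take each kind of worsening of a baseline condition and see what each rule requires.

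| Worsening of a baseline condition | 8.3 deterioration sentence | Other provisions | Result |
|---|---|---|---|
| Judged related | Recorded | Recorded (8.1, 8.2.2) | Agree |
| Judged unrelated, serious | Not an AE | Reportable (8.1, 8.1.1, 8.4.2) | Conflict |
| Judged unrelated, non-serious, head-and-neck or respiratory | Not an AE | Collected (8.1) | Conflict |
| Judged unrelated, non-serious, elsewhere | Not an AE | Outside the 8.1 scope, but documented under 8.2.2 and the other 8.3 sentence | Conflict, also between 8.1 and the other 8.3 sentence |

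All three unrelated cases conflict, and no provision ranks the rules.

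**Effect on the 10.4.4 summaries.** Incidence there is the number and percentage of subjects with at least one event in a class. An unrecorded worsening lowers the figure only when that subject has no other recorded event in the class. The direction can only be downward, for overall AEs and, if a serious worsening is missed, for SAEs. The severity summary takes each subject's most severe event, so it can also shift.

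**Effect on the primary safety endpoint.** The endpoint (4.2.1) counts nasal procedure- and device-related events through 6 months. Worsening judged related passes the 8.3 condition, so in general the endpoint keeps it. One gap remains. Section 10.4.4 counts possibly, probably and definitely related events as device-related, while 8.2.2 describes the possible grade as not likely. Section 8.3 does not say which grades satisfy its condition, or whether procedure there includes concomitant septoplasty and turbinate reduction. A site that takes related to mean probable or definite would drop a possibly related worsening that the analysis would have counted.

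**Effect on review.** Section 8.6 and 10.4.7.1 provide for review of AEs by the Medical Monitor, joined by the Scientific Advisory Board for reported SAEs. An event that is not recorded reaches neither. Full source verification (section 9) covers endpoint data and adverse device effects through 6 months, so a worsening set aside as unrelated is not a stated target of monitoring.

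**The case against.** The strongest reply is that the rest of the protocol already protects against loss. Sections 8.1, 8.1.1 and 8.4.2 require every SAE, and 8.1.1 names new hospitalization explicitly. Section 8.2.2 tells sites to report when in doubt. This stands: a reader might infer that serious worsening will be lost, but the documents support only that it could be, if a site decides under 8.3 that the event is not an AE and never reaches the seriousness test.

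A reader might also infer that the primary safety endpoint is biased low. That is not shown. It counts related events, and 8.3 lets related worsening through. The Medical Monitor is given AE review and expectedness (8.2.3), but causality belongs to the examining clinician, and no step for reclassifying it is described. Only the undefined threshold leaves the endpoint exposed.

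Nor are the data beyond recovery. NOSE and VAS are collected at every follow-up through 24 months, nasal examinations through 12 months with endoscopic grading at 6 months, and allergic rhinitis status at 1, 3, 6 and 12 months. Worsened obstruction would show there, though without an AE severity, seriousness or causality grade.

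Finally, it would be wrong to say that most plausible nasal harms are worsenings of a baseline condition. The AE types in 10.4.4 are largely new events, such as hematoma, extrusion, retrieval and migration. Crusting or loss of smell appearing for the first time would not fall under the baseline rule at all.

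None of this removes the contradiction. It limits what follows from it.

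**Conclusion.** The point holds as an internal contradiction with a possible, one-sided effect on AE ascertainment. As written, 8.3 makes relatedness a condition for recording worsening of a baseline condition. Sections 8.1, 8.1.1, 8.2.2 and another sentence of 8.3 say otherwise.

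A site following the 8.3 sentence could leave unrecorded a worsening of obstruction, allergic rhinitis or septal/turbinate disease that it considers unrelated, and possibly a serious worsening. Overall AE incidence, and possibly SAE incidence, could then be too low, and the unrelated judgement could not be reviewed. The primary safety endpoint is at risk only where a site's threshold for relatedness is stricter than the analysis cut.

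The size cannot be computed. For obstruction the rule reaches the whole cohort, but the documents give neither a rate of AE-level worsening nor the share that would be judged unrelated. The conclusion assumes that at least some sites would apply the specific 8.3 sentence ahead of the general rules. Confidence is high for the contradiction and lower for its practical effect. The correction should be made because it is cheap and concerns safety recording.

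**What to change.** 1. In 8.3, delete the clause that makes relatedness a condition for recording deterioration. State that worsening of a baseline condition is recorded as an AE under the full 8.1 scope: all SAEs, ADEs and SADEs; all non-serious device- and procedure-related AEs; all non-serious head-and-neck and/or respiratory AEs. Relationship is then graded under 8.2.2. All three arms need to be named, so that related non-serious worsening elsewhere in the body is not dropped.
2. Reconcile the 8.3 sentence on documenting all AEs regardless of relationship with that scope, so that sites have one rule.
3. Reconcile 8.1, which runs SAE collection to the end of participation, with 7.1.4 and the schedule in 7.7, which limit collection to adverse device effects after 12 months.

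The cost is a protocol wording change, a site memo, somewhat more AE forms and slightly higher reported AE counts. The current text gives no threshold for deterioration. Once the relatedness condition goes, that gap matters more, because ordinary fluctuation in obstruction or seasonal allergy could generate forms. The sponsor should say what counts as deterioration when making the change.
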